Study Design	Open label comparison of two proven interventions in COPD to assess responsiveness of exercise tests
Study Participants	Adult COPD subjects
Planned Sample Size	 Phase 1, n=60 (to allow for drop out & interim analysis after the last visit of patient #50) Phase 2, further 79 (allowing for a 25% drop out) Total recruitment of 139 subjects
Follow-up duration	Six weeks
Planned Study Period	17 Months – Phase 1 (March 2013 – December 2014) 24 Months – Phase 2 (December 2015 – November 2017)
Aims	To assess the responsiveness of a range of exercise tests in relation to six minute walk
Outcome measures	ISWT, ESWT, 6MWT, endurance cycle, incremental cycle, SPPB, PROactive, Accelerometery.

Aim

By conducting a comprehensive comparison of exercise tests commonly employed to assess functional capacity in subjects with COPD we aim to secure a wider understanding of the relative properties (stability and sensitivity) of the these tests to guide clinical trial outcome selection. The study will produce data which are sufficiently robust to provide information for the regulatory bodies regarding the assessment of activity limitation in COPD for future clinical trials.

Hypothesis

The 6MWT is the least sensitive test that can be employed in the assessment to response to treatment of either pulmonary rehabilitation or bronchodilator therapy.

Background

Exercise outcomes are required to capture outcomes relevant to subjects missed by spirometry

Traditional measures of airflow obstruction such as FEV_1 offer an inadequate reflection of the impact of COPD and are not influenced by otherwise effective therapy, particularly pulmonary rehabilitation (1, 2). Conversely exercise tests are used to assess activity limitation (disability) and are capable of improvement after various therapies, including bronchodilators (3). Several exercise tests have been described for this purpose. The existing tests vary in the required physical environment (laboratory vs. field), exercise platform (cycling vs. walking) or protocol (maximal vs. endurance, paced vs. self-paced). There has been no comprehensive comparison of the relative reproducibility and sensitivity of these tests when performed concurrently.

Existing tests span a range of complexity

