- Health status measures
 - The CAT questionnaire This is a short 8 item questionnaire designed to assess the impact of the disease upon the individual. It is simple to complete and will take participants approximately 2 minutes to answer the questions, and is responsive to PR (29).
 - Chronic Respiratory Disease –Self Reported- This standardised and established questionnaire has 4 domains, dyspnoea, fatigue, mastery (feeling of control over disease) and emotion (30, 31). The dyspnoea component will be the primary outcome, but the study will be powered to detect important changes in mastery. This study will be powered using data from our pilot data. A MCID of 0.5 has been established by the original authors for each domain (32). It has been frequently and successfully employed in both primary and secondary care studies (particularly rehabilitation and medication management) with no ceiling effect in milder subjects.

⁴ Glenfield use PowerLab software (ADInstruments, New Zealand)

St George's Respiratory Questionnaire (SGRQ) – This established, disease specific health related quality of life questionnaire has been validated and standardised internationally as a sensitive measure of impaired health in COPD (33, 34). Three domains are constructed from a 50 item self-administered questionnaire; these are symptoms (eight items), activity (16 items) and impacts (26 items). Domain scores are calculated using algorithms with subscale scores and total scores documented from 0 (no impairment) to 100 (maximal impairment). An MCID of 4 units has been suggested as an acceptable response to intervention in COPD (35).

Protocol (see also Figure 1)

It should be noted the purpose of the study is to test the outcome measures and not the intervention. The use of, two interventions will allow the investigators to understand performance of the test in the two different scenarios over two differing timescales.

Test Interventions- There would be 2 test interventions – long-acting muscarinic antagonist bronchodilator therapy (LAMA) and standard pulmonary rehabilitation. These would be offered in two parallel groups over six weeks. In addition there will be a control group assessed over a comparable time period. Those subjects randomised to the bronchodilator and control groups will receive rehabilitation on a clinical basis after the study (figure 1). All assessments will be performed by an assessor blinded to treatment allocation.

Intervention 1

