
Based on the interim results, approximately 90 evaluable subjects in the LAMA arm are required to provide >80% power to detect a 50sec change from baseline, assuming a standard deviation of 160sec and a one-sample, two-sided t-test at a significance level of 0.05. To account for a potential 25% dropout rate in Phase 2, 120 subjects will be randomized to the LAMA treatment arm.

The table below shows the number of evaluable subjects needed from the LAMA arm in Phase II to detect a 50 second change from baseline at either 80% or 90% power, given different estimates of standard deviation.

Table of one sample t test power to acted sosse change from baseline					
N needed	SD = 130	SD = 140	SD = 150	SD = 160	SD = 170
Power =80%	56	64	73	83	93
Power =90%	73	85	97	110	124

 Table 3. One-sample t-test power to detect 50sec change from baseline

As changes from baseline are not expected in a control arm, and pulmonary rehabilitation has demonstrated effects in all exercise measures in the interim analysis, these arms will serve mainly to provide additional study sensitivity data. Thus, the randomization allocation will change from 2:2:1 to 4:1:1 to make sufficient within-group comparisons. 30 subjects will be randomized to receive pulmonary rehabilitation and 30 subjects will be randomized as controls in order to provide 22 additional evaluable subjects, plus 8 more to account for a potential 25% dropout rate, in each arm. In total, 180 subjects will be randomized to Phase 2.

2. Sample size re-estimation

WP4 Exercise outcome study

The revised power calculation is aligned with the actual data from the interim analysis. This new calculation is based on a mean change in the ESWT of 60±160 seconds (as per interim analysis) with 80% power and alpha of 5%. A total of 58 subjects are required in the LAMA group and allowing for 25% attrition, a total of 78 recruited subjects are required in the LAMA (table 4). As stated above there is no specific target allocation for placebo or PR in phase 2. We propose to maintain the control arm to provide a negative control to the LAMA arm and reduce the study bias, and allow us to maintain blinding.

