Sensitivity study - Comparison between the exercise test outcome measures will be made at two separate time points, baseline and 6 weeks. The primary measure for each test will be the variable that is most commonly reported e.g. distance /time/peak oxygen consumption. We will assume that an MCID of 25m is meaningful for 6MWT (15), and assess the ability of other tests to predict this change. Attention will be paid to both floor and ceiling effects.

Data accumulated from individuals offered rehabilitation upon completion of either the control or LAMA arm will be analysed after the main trial has been completed. This data will allow a repeat measures analysis comparing the relative effect of two interventions upon the exercise tests. This is a secondary planned analysis.

Opportunities for sub studies

a) MCID - This study would afford the opportunity to test this assumption and identify an MCID for the exercise tests employed in this study. We will report the MCID in one of two ways, we will employ an anchor based approach and report a statistically general distribution based approach. In addition by relating observed changes in exercise performance to the CRQ we will aim to generate a further MCID for the exercise tests, since it has recently been suggested that an MCID may differ depending on the context and nature of the intervention (37).

Practical Considerations & timescale to do (plus Gant chart)

Three sites should be adequate to recruit the required number of subjects. We estimate that it would take 36 months to complete this study, the pilot study will be conducted over the first year with a recruitment target of n=50. After this pilot phase recruitment will be extended to 3 sites.

Pilot study

Allow 3 months to gain necessary recruitment approval, advertise and recruit staff. To confirm whether MHRA approval required. Completion of ethics submission.

Months 1-3	Finalise ethics approval/set up database & randomisation system with Leicester & staff training as required.	
Month 3-24	Recruit 50 subjects to study – completion of baseline measures	
Month 24-30	Completion of data collection and preliminary analysis	
Month 24-30	Change ethics for multi-centre study	
Month 30-33	Recruitment in place for other sites (2/3)	

Study extension (planned recruitment – 180 participants – 90 per site). Recruitment will continue seamlessly at the Leicester site but allow for 21 months recruitment from the end of the pilot data).

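### The hypothesis ranks the 6MWT against other tests, but the 80% power covers only ESWT change from zero in the LAMA arm, the one specific cross-test analysis uses the 6MWT as its yardstick, and CRQ is elsewhere called primary.

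*Protocol*

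**What the plan says.** **Aim and hypothesis.** The summary table gives the aim as "To assess the responsiveness of a range of exercise tests in relation to six minute walk". The hypothesis is that "The 6MWT is the least sensitive test that can be employed in the assessment to response to treatment", and it covers both pulmonary rehabilitation and bronchodilator therapy. The Method and Protocol sections both say that the tests are under study, not the interventions.

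**Sample size.** Under the heading 2. Sample size re-estimation: "This new calculation is based on a mean change in the ESWT of 60±160 seconds (as per interim analysis) with 80% power". Then: "A total of 58 subjects are required in the LAMA group and allowing for 25% attrition", 78 are to be recruited. Table 4 labels this a one-sample t-test. The preceding 50 s calculation gives the sidedness: "assuming a standard deviation of 160sec and a one-sample, two-sided t-test at a significance level of 0.05".

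**Analysis Plan.** Changes within each group are tested by paired t or Wilcoxon signed rank. The sensitivity and specificity of the other measures for the MCID change are also planned. The Sensitivity study paragraph adds: "Comparison between the exercise test outcome measures will be made at two separate time points, baseline and 6 weeks". It then takes 25 m as the meaningful change in 6MWT and asks how well the other tests predict it.

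**Health status measures (CRQ-SR).** "The dyspnoea component will be the primary outcome, but the study will be powered to detect important changes in mastery". The next sentence there says that pilot data will supply the power calculation.

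**The concern.** The question is comparative: does the 6MWT respond less than the other tests in the same patients? The quantity that was powered is not. The ESWT change can differ from zero whether the 6MWT responds less, equally or more, so reaching the powered target says nothing about the hypothesis.

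The one cross-test analysis described in detail has a structural problem. If a 25 m change in 6MWT is the truth, a patient who improves on another test but not on the 6MWT is counted as a false positive for that other test. A more responsive test is penalised for being more responsive.

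The CRQ sentences give the reader a different primary outcome and a power claim that nothing in the document supports. The results are meant for regulators choosing trial outcomes, so what the 80% covers should be unambiguous.

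**Working it through.** **1. The plan's own figure.** Inputs: mean change 60 s, SD 160 s, two-sided alpha 0.05, n = 58.
- Standardised change = 60/160 = 0.375.
- Noncentrality = 0.375 × √58 = 2.856, with 57 degrees of freedom and critical t = 2.002.
- Power from the noncentral t = 80.2%; at n = 57 it is just under 80%. So 58 is right.
- 58/0.75 = 77.3, so 78 recruited is right.

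The other entries of Tables 3 and 4 also reproduce. The superseded 6MWT calculation (25 m, SD 100 m) gives 128 by the same one-sample test, so it too was a change against zero and not a comparison of tests.

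**2. What that power covers.** One test (ESWT), one arm (LAMA), null value zero. Neither the 6MWT nor the rehabilitation arm enters it, although the hypothesis names both.

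**3. What a comparison would need.** Let S₁ and S₂ be the standardised response means (SRM, mean change divided by SD of change) of ESWT and 6MWT, and ρ the correlation between the two changes. In the same n patients,

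Var(S₁ − S₂) ≈ [2 + S₁²/2 + S₂²/2 − 2(ρ + S₁S₂ρ²/2)] / n

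Power is approximately Φ(z − 1.96), with z = (S₁ − S₂)/SE. The difference detectable with 80% power is 2.80 × SE.

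S₁ = 0.375 is the planning value above. The protocol gives neither ρ nor S₂ for this trial, so both are assumptions:
- ρ from 0 to 0.7;
- S₂ = 0.25 (25/100, the superseded planning values) or S₂ = 0 (no 6MWT response at all).

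Example with ρ = 0.5, S₂ = 0.25: the bracket is 2 + 0.0703 + 0.0313 − 2(0.5 + 0.0117) = 1.078. SE = √(1.078/58) = 0.136, z = 0.125/0.136 = 0.92, power 15%.

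| ρ (assumed) | 0 | 0.3 | 0.5 | 0.7 |
|---|---|---|---|---|
| SE at S₂ = 0.25 | 0.190 | 0.160 | 0.136 | 0.106 |
| Power, S₂ = 0.25 | 10% | 12% | 15% | 22% |
| Power, S₂ = 0 | 51% | 65% | 79% | 94% |
| Detectable SRM difference, 80% power | 0.53 | 0.45 | 0.38 | 0.30 |

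A second method, a paired t-test on standardised changes with SDs taken as known, gives 10% to 23% for S₂ = 0.25 and 51% to 95% for S₂ = 0. With S₂ = 0.19 (363 − 344 = 19 m over 100 m, from the Table 1 study used for planning) it gives 17% to 43%.

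**4. CRQ.** The Power calculation section and both re-estimation sections contain calculations for 6MWT and ESWT only. None uses a CRQ domain, a CRQ standard deviation or the 0.5-unit MCID. The summary table's list of outcome measures does not include the CRQ.

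**The case against.** Three objections have force.

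*The tests are compared.* A reader might infer that no planned analysis compares the tests. The documents do not support that. The Sensitivity study paragraph announces a comparison, sensitivity and specificity are planned, and MCIDs for the tests are to be derived. Nor does any section say that tests will be ranked by which p-values fall below 0.05, or that the trial is positive if the ESWT changes. Reading the comparison at two time points as purely cross-sectional is also only one reading; it may mean pre/post change.

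*The statistic may be in the SAP.* It may, and the absence of a named responsiveness index is not the finding here. An SAP cannot, however, turn power for ESWT against zero into power for the hypothesis, or remove the CRQ statement. The use of the 6MWT as reference is stated in the protocol, not left open.

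*The trial is not shown to be underpowered.* A reader might take the 10% to 22% row as the trial's true power. That would go too far. The 25 m is an MCID and planning target, not an expected response. The 100 m SD lies close to that study's SDs of 6MWT distance in Table 1 (105 and 98), which are not SDs of change. The correlation is assumed. If the 6MWT hardly responds, power may be adequate.

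**Conclusion.** The point holds in three parts, none of which depends on assumed values:
- The 80% power is correct for LAMA-arm ESWT change against zero and does not address the hypothesis.
- The one cross-test analysis described specifically treats the 6MWT as the standard, so it cannot show the 6MWT to be the least sensitive test.
- The statement that CRQ dyspnoea is primary and that the study is powered for mastery has no calculation behind it and conflicts with the sample-size sections.

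The size of the power gap is illustrative only: about 10% to 94% at 58 completers, resting on assumed correlations of 0 to 0.7 and an assumed 6MWT SRM between 0.25 and 0. The range shows that the protocol gives no basis for claiming 80% for its own question. It does not show that the trial must fail to answer it.

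**What to change.** 1. In Health status measures, delete or correct the sentences that make CRQ dyspnoea primary and claim power for mastery.
2. In the re-estimation section, state that the 80% applies only to ESWT change from zero in the LAMA arm and is not power for the hypothesis.
3. In the Sensitivity study paragraph, add as the analysis of the hypothesis a within-patient contrast of standardised change between each test and the 6MWT. Use patients with both tests, give 95% confidence intervals (for example by bootstrap over patients), and report by intervention arm. Keep the 25 m prediction analysis as descriptive.
4. State the expected precision at 58 completers as illustrative: a detectable SRM difference of about 0.53, 0.45, 0.38 or 0.30 for assumed correlations of 0, 0.3, 0.5 or 0.7.

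This changes wording and analysis only and needs no new data. The cost is a less favourable statement of precision for the real question. Correction for control change and adjustment for multiple tests are optional and would lower precision further. For example, 27 controls recruited leave about 20 after 25% attrition. At ρ = 0.5 with no mean change in controls, they add 2(1 − 0.5)/20 = 0.05 to the variance, so SE rises from 0.136 to √(0.0186 + 0.05) = 0.26 and the detectable difference from 0.38 to about 0.73.

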- b. 6 MWT (performed twice with a 30 min rest in-between)
- c. ISWT (performed twice with a 30 min rest in-between)
- d. Strength testing (QMVC)

Visit 3 (next day)

Three exercise tests will be conducted in random order. There will be at least 30 minutes rest between each test.

- e. ESWT (85% peak performance)
- f. Cycle endurance test (85% peak performance)
- g. SPPB

Retesting after completion of the 6 week intervention (visits 4 and 5), will comprise the following measures presented in the same order as baseline (visits 2 and 3). These tests will be completed by a blinded assessor, blind to the intervention and previous results. Two activity monitors will be given, to be worn during visits 4 & 5 and for a further 7 days (24 hours a day).

- 1. ISWT
- 2. 6MWT
- 3. ESWT, at same level as baseline
- 4. Maximal incremental cycle test
- 5. Endurance cycle test, at same workload level and RPM as baseline
- 6. SPPB
- 7. Strength testing (QMVC)
- 8. Health Questionnaires

At the completion of the interventions a global rating scale of change will be reported for each exercise test. This will allow the description of the MID using anchor and distribution based methods. The global rating scale will identify two levels of change (a little improvement and a greater level of improvement). The scale employed will be one recently described by Pepin et al (37) describing the MCID for the ESWT.

Power calculation

In order to calculate a sample size a literature search was conducted using the search terms Tiotropium and six minute walk (and variants e.g. 6MWT) to identify studies giving an estimate of the likely benefit of the drug. Results found are shown in Table 1.

n	Blinded Assessor	Baseline 6MWT (mean (SD))	Tiotropium 6MWT (mean (SD))	Reference	notes
30	n	344 (105)	363 (98)	Fernandes 2010 (38)	Additional use of LABA
38	У	490 (67)	+6 (19)	Oga 2000 (12)	Additional use of Oxitropium
41	n	403 (20)	429 (17)	Fujimoto (39)	-
38	n	222 (5)	+13.5 (2)	Um(40)	-
44	У	415 (75)	429 (70)	Okudan(21)	Single dose (after 120 minutes)

Table 1: Properties of trials investigating Tiotropium with the 6MWT.

Based on these data [name] (Statistician to the Royal Brompton hospital Biomedical Research Unit) estimated the following sample sizes for achieving an increase in 25m in 6MW with 80% power and p=0.05.

Reference	Tio 6MWT (SD of Change From BL)	Estimated Sample size
Fernandes 2010	100 *	128
Oga 2000	19	7
Fujimoto	20 *	7
Um 2007	2	1
Okudan 2006	75 *	73

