Table 4: One-sample t-test power to detect 60sec change from ba	seline
---	--------

N needed	SD = 130	SD = 140	SD = 160
Power =80%	39	45	58

Randomisation allocation recruitment at Glenfield hospital, Leicester, can be seen in Table 5 (April 2015 – September 2016).

Allocation and Ratio	Control	PR	LAMA
1.2.2 (actual)	16	32	32
1.1.4 (actual)	2	2	10
Current allocated totals	18	34	42
Number required for LAMA (ESWT response of 60±160 sec with 80% power and alpha of 5	-	-	78 recruited 58 completed
New allocation for recruiting n=78 in LAMA (1:0:4)	9	0	36
Total recruited to trial	27	34	78

Table 5: Randomisation allocation over	er time
--	---------

To ensure rigor is maintained a randomisation allocation of 1:0:4 would recruit a further 9 subjects to the control group and a further 36 into the LAMA group.

Analysis Plan

All exercise test data will be analysed on a per protocol basis. All data will be assessed for normality and analysed using appropriate parametric or non-parametric statistics. Significance will be set at p<0.05 and differences will be expressed as mean and standard deviations (SD) or 95% confidence intervals.

Data will be presented as mean (SD) or median (IQR). Comparison of values obtained within the treatment(s) and the control groups will be made using a paired t test or the Wilcoxon signed rank test. All tests will be 2 tailed. Additional analysis will be done to determine the sensitivity and specificity of the other measures to detect the change in MCID. Similarly the sensitivity and specificity of the failure to detect change in the placebo will also be determined.

Reproducibility study – The baseline data will examine the test-re test reproducibility of each of the tests employed, including measures of strength. The primary variable for each test will be the conventional measure of performance. Data will be compared in two ways, firstly the intra-class correlation (ICC) will be reported and secondly limits of agreement using Bland & Altman techniques (41). The Bland & Altman plot will allow us to check the data for stability across a range of performance.

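### The one explicit sensitivity rule uses a 25 m change in the 6MWT as the reference and scores only the other tests, so that component cannot support the hypothesis that the 6MWT is the least sensitive test

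*Protocol*

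**What the plan says.** The Hypothesis section states: "The 6MWT is the least sensitive test that can be employed in the assessment to response to treatment of either pulmonary rehabilitation or bronchodilator therapy". The synopsis gives the aim as "To assess the responsiveness of a range of exercise tests in relation to six minute walk".

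The Analysis Plan then contains:

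- **Sensitivity study, reference:** "We will assume that an MCID of 25m is meaningful for 6MWT (15), and assess the ability of other tests to predict this change".
- **Analysis Plan, metric:** "Additional analysis will be done to determine the sensitivity and specificity of the other measures to detect the change in MCID". The next sentence adds a specificity-type analysis of failure to detect change in the control arm, which it calls placebo.
- **Sensitivity study, opening sentence:** "Comparison between the exercise test outcome measures will be made at two separate time points, baseline and 6 weeks". Each test contributes its most commonly reported variable. No statistic for the comparison is given.
- **Within groups:** "Comparison of values obtained within the treatment(s) and the control groups will be made using a paired t test or the Wilcoxon signed rank test".

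Outside the Analysis Plan's main text, two possible anchors are collected. Under Testing procedure, "At the completion of the interventions a global rating scale of change will be reported for each exercise test", for use in deriving minimal important differences. The sub-study section relates exercise changes to the CRQ to obtain further MCIDs. Neither is assigned as the reference for sensitivity.

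**The concern.** The hypothesis is about the 6MWT, but the 6MWT is the one test this rule does not evaluate. The metric is defined for the other measures, and the event they must detect is a 25 m change in the 6MWT. If a patient truly improves, and this shows on the ESWT or the cycle test but not as 25 m on the 6MWT, the disagreement is charged to the ESWT or cycle test. Under the hypothesis, those are the very patients who should show the 6MWT's weakness.

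The protocol intends the results to guide outcome selection in future trials and to go to regulators. A table of sensitivities and specificities built on this rule could be read as showing that the other tests perform poorly, when it shows only how far they agree with the 6MWT.

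**Working it through.** **1. The plan's own figure.** The final sample size is for a different question: a one-sample, two-sided t-test of ESWT change in the LAMA arm (60 s, SD 160 s, 80% power, alpha 5%). The noncentral t calculation gives 58 evaluable (power 0.802), and 58/0.75 = 77.3, so 78 recruited. Both agree with the protocol. This tests ESWT change against zero, not ESWT against 6MWT.

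**2. By construction.** Let the reference be positive when 6MWT change is at least 25 m. Scored against itself, the 6MWT has sensitivity 1.00 and specificity 1.00 for any data. No other test can exceed that.

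**3. What a perfect competitor would score.** Assumed inputs, not in the protocol: a proportion p of patients truly improve, the 6MWT detects this with sensitivity Se and specificity Sp, and errors are independent. A perfect test's apparent sensitivity is then the 6MWT's positive predictive value, and its apparent specificity is the negative predictive value:

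- Apparent sensitivity = Se·p / [Se·p + (1−Sp)(1−p)]
- Apparent specificity = Sp(1−p) / [Sp(1−p) + (1−Se)p]

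| Se / Sp | p | Apparent sensitivity | Apparent specificity |
|---|---|---|---|
| 0.60 / 0.75 | 0.5 | 0.30/0.425 = 70.6% | 0.375/0.575 = 65.2% |
| 0.60 / 0.75 | 0.3 | 50.7% | 81.4% |
| 0.60 / 0.75 | 0.7 | 84.8% | 44.6% |
| 0.80 / 0.85 | 0.5 | 0.40/0.475 = 84.2% | 0.425/0.525 = 81.0% |

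**4. Does a better competitor collect more false positives?** Not in this model. With Se 0.60, Sp 0.75 and p = 0.5, a competitor only as good as the 6MWT has apparent sensitivity 0.706×0.60 + 0.294×0.25 = 49.7%. Its apparent specificity is 0.652×0.75 + 0.348×0.40 = 62.8%. The perfect test, at 70.6% and 65.2%, has fewer false positives.

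At a fixed cut-off the picture can differ. Assume a 6MWT standardised response of 0.2, SD of 6MWT change 75 m, correlation of changes 0.3, and a competitor cut-off of 0.3 SD. Raising the competitor's standardised response from 0.375 to 0.8 moves its sensitivity from 0.636 to 0.785 and its specificity from 0.556 to 0.384. Sensitivity + specificity − 1 goes from 0.192 to 0.169, so a clearly more responsive test gains nothing overall.

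**5. AUC and the role of correlation.** Assume half the patients improve and errors are normal. The 6MWT shifts by 0.5 SD and the competitor by 1.0 SD. True AUC = Φ(shift/√2): 0.64 for the 6MWT and 0.76 for the competitor. Against a dichotomised 6MWT reference, simulation gives for the competitor:

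| Error correlation | Apparent AUC (true 0.76) |
|---|---|
| 0 | 0.55 |
| 0.3 | 0.67 |
| 0.5 | 0.75 |

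With independent errors, the competitor's apparent AUC at shifts 0.5, 1.0 and 2.0 is 0.527, 0.552 and 0.584: compressed, but in the right order. The recovery to 0.75 at correlation 0.5 is partly shared noise. Rerunning the same model with a competitor no better than the 6MWT (shift 0.5, true AUC 0.64) also gives about 0.75. The score then reflects agreement with the 6MWT more than responsiveness.

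**The case against.** The 25 m rule is one part of the plan, not all of it. The Sensitivity study opens with a comparison between the tests at baseline and six weeks. Within-group change is tested for every test, including the 6MWT, and the resulting changes can be set side by side. The control-arm analysis uses allocation as a reference that does not depend on the 6MWT. The sub-study treats 25 m as an assumption to be examined. Relating other tests to an established 6MWT threshold also fits the stated aim of responsiveness in relation to the 6MWT. Finally, the choice of a between-test statistic is often left to an SAP, which is not shown.

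Most of this stands, and it limits the point. A reader might infer that the trial cannot answer its question whatever the data show. The documents do not support that, because the other planned analyses can inform it. A reader might also infer that the more responsive a competitor is, the more false positives it must collect. That holds only in some settings, such as a fixed cut-off, and fails in the simple model above.

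What the objection does not remove is the rule itself. The protocol fixes the 6MWT as the reference and defines the metric for the other measures only. That is a stated choice, not a detail left open. Comparing tests in relation to the 6MWT requires scoring the 6MWT too. And one test reaching p<0.05 within a group while another does not is not a comparison of the two.

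**Conclusion.** The point holds for the 25 m component. That analysis cannot support the hypothesis that the 6MWT is least sensitive, because the 6MWT is perfect by construction and disagreements count against the other tests. This needs no assumption about the data, only the diagnostic reading of the rule, which the sensitivity and specificity wording supports.

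The size of the distortion is not known. It generally lowers the competitors' apparent accuracy, but the amount depends on the correlation between tests, which the protocol does not give. In the illustration a true AUC of 0.76 appears as anything from 0.55 (independent errors) to 0.75 (error correlation 0.5). The 0.55 is the independence extreme and should not be quoted alone, since these are related tests in the same patients.

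The within-group tests, the unspecified between-test comparison and the control-arm specificity can still bear on the hypothesis. None is stated as a head-to-head contrast with the 6MWT.

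**What to change.** Evaluate every test, including the 6MWT, on the same footing:

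1. **Main contrast.** Within the LAMA arm and within the PR arm, compare standardised response (mean change divided by SD of change) between the 6MWT and each other test. Pair the comparison within patients and give 95% CIs.
2. **Support.** Report sensitivity, specificity and AUC for all tests, 6MWT included, against a common reference already collected: CRQ-SR dyspnoea change of at least 0.5 (the MCID the protocol cites), and active versus control allocation. The choice of paired method for comparing AUCs is open.
3. **Global rating.** It is given separately for each exercise test, so use it only within its own test and not as a common reference.
4. **The 25 m rule.** Keep it as a descriptive cross-tabulation of agreement with the 6MWT.

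The cost is analysis wording only, with no new data. There are three drawbacks. The CRQ is an imperfect anchor, and the Schedule of Visits takes questionnaires at visit 1 but the exercise baseline at visits 2 and 3, so the two changes do not span the same interval. The allocation contrast is imprecise: Table 5 gives 27 recruited controls, or about 20 evaluable at 25% attrition (27×0.75 = 20.25). The precision of the main contrast cannot be stated in advance, because the protocol gives neither the correlation between test changes nor the SD of 6MWT change in this trial. The interim data could supply both.
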